8.2 Sample size estimate

The number of VOCs is assumed to have a negative binomial distribution with shape parameter 0.8. The mean number of crises per year is assumed to be 2.0 in the placebo group with reduction of 50% in the ticagrelor group. Patients will be randomised to 1:1 ratio and with minimum follow-up of 12 months and average follow-up of 18 months, 154 patients provide about 90% power for a 2-sided test of the mean number of crises for ticagrelor versus placebo, at significance level 5%. Allowing for dropouts, the sample size is increased to 182. The calculations were based on simulation with 5,000 repetitions.

Scenarios and simulations were evaluated to assess the risk with shorter and longer mean follow-up time. To ensure that the study is adequately powered the recruitment rate will be monitored and the sample size may be adjusted to a maximum of 200 patients. With a mean follow-up time of 13 month, 200 patients will provide 90% power to detect a reduction of 50% in the ticagrelor group.

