3.1.4 Treatment Period

The double-blind randomised treatment period comprises of regular scheduled in-clinic visits as well as regularly scheduled telephone visits. The treatment period starts at randomisation (Visit 2) through the end of study (EOS) visit regardless of whether the patient prematurely discontinues study treatment. Refer to Section 3.1.4.1 for details on EOS visit. For patients who prematurely discontinue from study participation within this period, the double-blind randomised treatment period is defined through to the last available visit/assessment date or date of premature study discontinuation, whichever is latest.

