4.2.5.1 Study Treatment Exposure

Total duration of study treatment exposure (days) by dose level and overall dose level (includes missed exposure days due to study treatment interruptions):

- Exposure (days) = (date of last dose of double-blind randomised study treatment – date of first dose of double-blind randomised study treatment) + 1

Where:

Date of first dose of double-blind randomised study treatment equals:

- Variable: *Start date of study drug administration*: Based on the EX eCRF, earliest administration date, at or after randomisation (Visit 2), at a given dose level and for each dose level received.
- By overall dose level: Overall earliest of the aforementioned first dose of study treatment administration dates, over all dose levels received.

Date of last dose of double-blind randomised study treatment equals:

- Variable: *End date of study drug administration*: As captured on the EX eCRF and is the latest administration date, on or after randomisation (Visit 2), at a given dose level and for each dose level received regardless of temporary study treatment administration discontinuation (study treatment interruptions).
- By overall dose level: Overall latest of the aforementioned last dose of study treatment administration dates, over all dose levels received. Patients may prematurely discontinue study treatment administration whilst continuing with scheduled assessments in the double-blind randomised treatment period. DOSDISC eCRF collects the variable, *date subject discontinued IP*. This date should equal the overall date of last dose of study treatment as captured on the EX eCRF but can be used in conjunction with EX data to accurately identify the overall date of last study treatment administration over all dose levels received in the double-blind randomised treatment period.

Total exposure years (across patients in a given treatment group) is defined as the sum of total double-blind randomised study treatment exposure (days) by overall dose level, including missed exposure days due to study treatment interruptions, for all patients in a given treatment group and is expressed in years as follows:

- Total exposure years (across patients) = Sum of (total study treatment exposure [days] by overall dose level)/360

Where:

Year = 360 days. .

Actual study treatment exposure (days) by dose level and overall dose level follows the same approach, however excludes all missed exposure days due to study treatment interruptions.

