4.2.6 Primary Efficacy Variable

4.2.6.1 Number of VOCs

The primary efficacy variable is the number of VOC events during the defined treatment period (refer to Section 3.1.4) and the primary analysis is to compare the VOC event rate of ticagrelor with placebo based on the intent to treat (ITT) principle. The primary efficacy analysis will be performed using FAS (refer to Section 2.1).

The null hypothesis is that the VOC event rate on ticagrelor is equal to the VOC event rate on placebo. The alternative hypothesis is that the VOC event rate on ticagrelor is not equal to the VOC event rate on the placebo, ie,

H_0 : Rate ratio (ticagrelor vs placebo) = 1

H_a : Rate ratio (ticagrelor vs placebo) \neq 1

The VOC event rate on ticagrelor will be compared to the VOC event rate on placebo using a negative binomial model for the primary analysis. The response variable in the model will be the number of VOC events experienced by a patient during the defined treatment period, regardless of premature discontinuation of study treatment. The model will include covariates of treatment group and baseline hydroxyurea use (Yes/No) as covariates.

The logarithm of the patient's observed follow-up time per defined treatment period expressed in years (where a year = 360 days) will be used as an offset term in the model to adjust for patients having different follow-up times.

The estimated treatment effect (ie, the rate ratio of ticagrelor versus placebo), the corresponding Wald 95% confidence interval (CI) and the p-value for the rate ratio will be presented. In addition, the VOC event rate and the corresponding 95% CI within each treatment group will be presented. The VOC event rate will be computed using the OM option in the LSMEANS statement of PROC GENMOD.

An estimated value of the rate ratio < 1 will favour ticagrelor. The estimated dispersion parameter will also be noted.

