4.2.6.2 Testing the Fit of Negative Binomial Distribution

The fit of the negative binomial distribution to the data will be tested by means of the Pearson goodness of fit test after estimating the parameters of the distribution and checking whether there are no convergence issues with the maximum likelihood estimation of the coefficients. The negative binomial model will be tested against the Poisson model in a likelihood ratio test to test the robustness of the model.

If the negative binomial distribution is not appropriate, a stratified Wilcoxon rank sum test will be used. As the stratified Wilcoxon rank sum test cannot be adjusted for the patient's follow-up time, the annualised number of VOC events will be used for the analysis rather than the number of VOCs as analysed for the primary efficacy. . By using annualised number of VOC events, it scales it allowing a comparison of VOC rates across patients with varying time in the study. Baseline hydroxyurea use (Yes/No) will be used as a stratification factor. Number of annualised VOC events is the count of VOC events experienced by a patient over the defined treatment period (refer to Section 3.1.5) as assessed by the investigator and collected on the VOC1 eCRF, multiplied by 360 days, and divided by the number of days in the defined treatment period.

$$\text{Num VOCs Annualised} = \frac{\text{Number of VOCs}}{(\text{defined treatment period end date} - \text{randomisation date}) + 1} * 360$$

A Wilcoxon rank sum test for each subgroup defined in Section 4.2.6.4 will also be presented. No stratification factor will be included in this analysis.

Median, median difference and 95% confidence interval for the median difference will be estimated using Hodges-Lehmann method. Summary statistics of the annualised VOC rate will also be presented.

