4.2.6.4 Subgroup analyses

To explore the uniformity of the detected overall treatment effect on the primary efficacy variable, subgroup analyses and statistical modelling including testing for interaction between treatment and covariates will be performed on the full analysis set for the factors below.

If there are issues with model convergence, only descriptive statistics by subgroup will be presented. Descriptive statistics by subgroup will be presented for all cases regardless of the model convergence. These analyses are exploratory and the results from these analyses will not affect the choice of terms used in the model for the primary analysis.

The following subgroups will be reported:

- Age by category:
 - ≥ 2 years to < 12 years at randomisation (Visit 2)
 - ≥ 12 years to < 18 years at randomisation (Visit 2)
- Number of VOC events within the previous 12 months prior to study enrolment at screening (Visit 1):
 - ≥ 2 to ≤ 4
 - > 4
- Baseline hydroxyurea use: Based on IxRS
 - Yes
 - No

- Sickle cell genotype: HbSS and HbSB⁰ Thalassaemia
- Geographic region:
 - North and South America (USA, Canada, Brazil)
 - Europe (UK, Turkey, Spain, Italy, Greece, Belgium)
 - Africa and Asia (Egypt, Ghana, India, Kenya, Lebanon, South Africa, Tanzania, Uganda)
- Gender: Male and Female
- Race as reported in [Appendix B Race Mapping](#):
 - White
 - Black or African-American
 - Asian
 - Other

If the negative binomial regression model is judged to be appropriate, then for each subgroup analysis separately, where sufficient data allows, a negative binomial regression model will be fitted including as covariates treatment group, subgroup main effect and the treatment-by-subgroup interaction. The p-value for the treatment-by-subgroup interaction will be presented.

The logarithm of the patient's observed follow-up time per defined treatment period expressed in years (where a year = 360 days) will be used as an offset term in the model to adjust for patients having different follow-up times.

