4.2.9.1 Adverse Events

Summary tables will include on-treatment/off-treatment AEs (refer to Section [3.4.1](#)) only, unless otherwise specified. That is, pre-treatment AEs will be included in the patient data listings only.

Separate overall summary tables will be produced for AEs on-treatment and off-treatment showing the number (n) and percentage (%) of patients with at least one AE in each of the following AE categories: Any AE, any AE causally related to study treatment, maximum AE intensity, any AE with an outcome of death, any SAE and discontinuation of study treatment due to AEs. The overall summary tables will be repeated by age group as follows:

- ≥ 2 years to <12 years at randomisation (Visit 2)
- ≥ 12 years to <18 years at randomisation (Visit 2)

AEs/SAEs will be summarised by MedDRA SOC and MedDRA PT by actual study treatment received and by the same age group as previously defined. Events will be sorted by international order for system organ class (SOC) and alphabetically for PTs within each SOC. For each SOC/PT, the number (n) and percentage (%) of patients reporting at least one event at each level of summarisation (SOC/PT) will be presented ie, for a patient with multiple occurrences of the same AE, the event will only be counted once per PT/SOC. Patients with events in more than one SOC/PT are counted once per individual SOC/PT.

Most common AEs will be summarised separately by MedDRA PT, where most common is defined as a frequency $> 5\%$ in either of the two treatment groups and sorted by decreasing frequency based on the ticagrelor treatment group. Similarly, for presentation of non-serious AEs. In addition, AEs will be summarised by MedDRA PT and causality/relatedness. If a patient reports multiple occurrences of the same AE, the patient will be summarised only for the most related. Similarly, by MedDRA PT and maximum reported intensity. If a patient reports multiple occurrences of the same AE, the patient will be summarised only for the maximum reported intensity. In case of missing causality/relatedness and/or intensity, a missing category will be presented per relevant PT.

The event rate per 100 patient years will be presented by treatment group, where:

Event rate per 100 patient years = (number of patients with AEs/total exposure years) \times 100 (refer to Section 4.2.5).

Where:

Year = 360 days.

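### The SAP counts a year as 360 days, so figures labelled per year print 1.44% below the same formula on a 365.25-day year; the rate ratio, its CI and all p-values do not change

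*SAP*

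**What the plan says.** The 360-day year appears in five places in the SAP:

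- **4.2.5.1, exposure years:** "Sum of (total study treatment exposure [days] by overall dose level)/360".
- **4.2.6.1, primary model:** the offset is the log of "observed follow-up time per defined treatment period expressed in years (where a year = 360 days". A VOC rate with 95% CI is reported for each arm. The secondary count and duration models in 4.2.8.1 to 4.2.8.8 refer back to this model and inherit the constant.
- **4.2.6.2, Wilcoxon fallback:** each patient's VOC count is "multiplied by 360 days, and divided by the number of days in the defined treatment period". The estimates on that scale are then described: "Median, median difference and 95% confidence interval for the median difference will be estimated using Hodges-Lehmann method".
- **4.2.6.4, subgroup models:** follow-up "expressed in years (where a year = 360 days) will be used as an offset term in the model".
- **4.2.9.1, AE rate:** "Event rate per 100 patient years = (number of patients with AEs/total exposure years", times 100, with the 360-day year stated again beneath the formula.

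SAP 4.2.2 uses 365.25 days for age at diagnosis and for years since diagnosis. Protocol 8.5.1 specifies log follow-up time without a year length. SAP section 6, which lists departures from the protocol, does not mention 360. The planning rate in Protocol 8.2 is annual: "The mean number of crises per year is assumed to be 2.0 in the placebo group".

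On the end of follow-up for patients who leave the study early, SAP 3.1.4 says: "the double-blind randomised treatment period is defined through to the last available visit/assessment date or date of premature study discontinuation, whichever is latest".

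**The concern.** A figure printed as a rate per year will be read as a rate per calendar year. With a 360-day year, person-time is overstated and each such rate is understated by a fixed proportion. Absolute VOC rates by arm, annualised counts, Hodges-Lehmann differences and AE rates per 100 patient years are the figures that others will quote, pool or set beside the planning rate of 2.0. The SAP gives no reason for 360 and uses a different year length elsewhere.

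The end-date rule raises a separate question about the same denominator. If a patient is lost and the discontinuation date is recorded some time after the last contact, the interval between counts as observed follow-up although nobody asked about VOCs in it. Protocol 8.5.1 treats unobserved time as missing at random. Here it would instead enter as mostly event-free time. Unlike the year constant, this could move the rate ratio if such losses differed between arms.

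**Working it through.** **1. The plan's own figure.** Inputs from Protocol 8.2: 154 patients randomised 1:1, rates 2.0 and 1.0 per year, mean follow-up 1.5 years, shape 0.8, two-sided 5%. With dispersion k,

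Var(log RR) = [1/(2.0 × 1.5) + 1/(1.0 × 1.5) + 2k]/77.

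- k = 1/0.8 = 1.25: 3.5/77 = 0.0455, SE 0.213. Then 0.693/0.213 − 1.96 = 1.29, so power is 90.2% (90.4% in 5,000 simulated trials).
- k = 0.8: power is 96.5%.

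The stated 90% is reproduced with k = 1.25, which is used in step 5.

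**2. The year constant.**

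- 360/365.25 = 0.98563, so rates are 1.44% low.
- 360/365 = 0.98630, so rates are 1.37% low against a 365-day year.
- 365.25/360 = 1.01458, so exposure years are 1.46% high.

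**3. What is printed.**

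| Figure | 365.25-day year | As the SAP prints it |
|---|---|---|
| VOC rate per year | 2.00 | 1.97 |
| VOC rate per year | 1.00 | 0.986 |
| Hodges-Lehmann difference | −1.00 | −0.986 |
| AE rate per 100 patient years | 50.0 | 49.3 |

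**4. What does not move.** For every patient, log(days/360) = log(days/365.25) + 0.01448. A constant added to every offset goes into the intercept, so the treatment coefficient, its standard error and the dispersion are the same. Multiplying all annualised counts by one positive constant keeps their ranks, so the Wilcoxon p-value is the same; the Hodges-Lehmann difference and its CI limits shrink by the factor 0.9856.

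One simulated dataset of 182 patients, fitted with both year lengths, agrees. The rate ratio was 0.5605 (0.3729 to 0.8424), p = 0.0054, dispersion 1.4377 and Wilcoxon p = 0.0876 both times. The placebo rate was 1.8897 with 360 days and 1.9172 with 365.25; the ticagrelor rate was 1.0592 and 1.0746.

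**5. Size against sampling error.** At the planned follow-up, the SE of the log placebo rate is √{[1/(2.0 × 1.5) + 1.25]/77} = 0.143. The shift is 0.01448/0.143 = 0.10 SE. The early termination (SAP 3.1.4.1) makes the planned follow-up out of date. Shorter follow-up in the same number of patients would raise the SE and lower this fraction. The 1.44% does not depend on follow-up.

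**6. AE rates.** Exposure ends at last dose (4.2.5.1), but on-treatment AEs run to last dose + 7 days (3.4.1). If the rate uses the on-treatment tally, then for an assumed 18-month exposure (548 days) the denominator omits 7/548 = 1.3% of the time at risk. That pushes the rate up, against the effect of the constant.

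**7. The end-date rule.** The documents do not give the number of silent losses or the length of the gaps. Two sets of assumptions show the range:

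- *Lighter.* Dropout 15.4% (28/182, the inflation in Protocol 8.2), a quarter of dropouts silent, gaps of 1 to 3 months. The placebo rate falls by 0.4% to 1.0%. A rate ratio of 0.50 becomes 0.500 to 0.501 with equal losses, 0.497 to 0.499 with 20% ticagrelor against 10% placebo dropout, and 0.501 to 0.504 with that reversed.
- *Heavier.* 10% to 20% lost, all with a gap, half-way through 548 days, gaps of 30 to 180 days. Rate factor = observed time/(observed + gap time). At the low end this is 520.6/(520.6 + 3.0) = 0.994, a fall of 0.6%. At the high end it is 493.2/(493.2 + 36.0) = 0.932, a fall of 6.8%. With losses 3:1 towards ticagrelor, the rate ratio is multiplied by 0.994 to 0.927.

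Both sets use the planned follow-up and assume no VOC is found in the gap.

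**The case against.** The case for leaving the SAP alone has real force. The 360-day year is declared wherever it is used and is applied to every event rate. The 365.25 in SAP 4.2.2 serves age and disease duration, so no two rates conflict. No planned test compares an arm's rate with 2.0, and labelling the rates per 360 days would also be accurate. All of this stands. It makes the point minor, but it does not turn a figure labelled per year into one per calendar year.

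A reader might infer that AE rates are 1.44% too low overall. The documents do not support that, because the 7-day difference in step 6 can work the other way.

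A reader might also infer that SAP 3.1.4 biases the primary result and that its rule should be replaced. That is not supported either. No passage dates a discontinuation after the last contact. Monthly telephone visits (Protocol Table 3) and eDevice alerts (Protocol 5.1.1.1) limit any gap. The on-treatment analyses in SAP 4.2.6.3 item 1 and Appendix E, where Table 6 has a row for patients lost to follow-up, stop at last dose + 7 days. Where last dose is dated at or before last contact, they leave at most 7 days of the gap. They answer a different question from the treatment-policy analysis, whose own imputations cover only counts after withdrawal, so a small opening remains.

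Ending primary follow-up at the last contact of any kind would be worse. VOC-triggered calls are contacts, so follow-up could end because a VOC occurred. Confirmed VOCs before withdrawal would also be dropped, although Protocol 8.5.1 includes all data up to withdrawal.

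**Conclusion.** The 360-day year is wrong as written, and the effect is small. Per-year VOC rates, annualised counts and Hodges-Lehmann differences with their CI print 1.44% below the same formula on a 365.25-day year, and exposure years print 1.46% high. The only assumption is the reference year; against 365 days the figure is 1.37%. For AE rates, 1.44% is the contribution of the constant alone. It would be a mistake to infer any effect on the treatment comparison: the rate ratio, its CI and all p-values are the same under either year length.

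The end-date rule is a conditional point only. It can add unobserved time to the primary denominator, but whether it does, and by how much, cannot be found from the documents. The ranges in step 7 rest on assumed inputs and on follow-up planned before the early termination. They support a sensitivity analysis and do not justify changing the primary rule.

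**What to change.** **Year length.** Replace 360 with 365.25 in SAP 4.2.5.1, 4.2.6.1, 4.2.6.2, 4.2.6.4 and 4.2.9.1. The secondary models follow through their reference to 4.2.6.1. This costs a SAP edit and one constant in the derivation code before database lock. It needs no new data and has no statistical downside.

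**End of follow-up (optional).** Leave SAP 3.1.4 as the primary rule. Add to SAP 4.2.6.3 a repeat of the primary analysis in which follow-up of patients lost to follow-up ends at their last scheduled site or telephone visit, not at a VOC-triggered call, and only VOCs with onset up to that date are counted. This costs one further model run on data already collected. The repeat uses slightly less person-time and leaves out any confirmed VOC after that visit, which is acceptable in a sensitivity analysis.

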4.2.6.2 Testing the Fit of Negative Binomial Distribution

The fit of the negative binomial distribution to the data will be tested by means of the Pearson goodness of fit test after estimating the parameters of the distribution and checking whether there are no convergence issues with the maximum likelihood estimation of the coefficients. The negative binomial model will be tested against the Poisson model in a likelihood ratio test to test the robustness of the model.

If the negative binomial distribution is not appropriate, a stratified Wilcoxon rank sum test will be used. As the stratified Wilcoxon rank sum test cannot be adjusted for the patient's follow-up time, the annualised number of VOC events will be used for the analysis rather than the number of VOCs as analysed for the primary efficacy. . By using annualised number of VOC events, it scales it allowing a comparison of VOC rates across patients with varying time in the study. Baseline hydroxyurea use (Yes/No) will be used as a stratification factor. Number of annualised VOC events is the count of VOC events experienced by a patient over the defined treatment period (refer to Section 3.1.5) as assessed by the investigator and collected on the VOC1 eCRF, multiplied by 360 days, and divided by the number of days in the defined treatment period.

$$\text{Num VOCs Annualised} = \frac{\text{Number of VOCs}}{(\text{defined treatment period end date} - \text{randomisation date}) + 1} * 360$$

A Wilcoxon rank sum test for each subgroup defined in Section 4.2.6.4 will also be presented. No stratification factor will be included in this analysis.

Median, median difference and 95% confidence interval for the median difference will be estimated using Hodges-Lehmann method. Summary statistics of the annualised VOC rate will also be presented.

4.2.6.3 Sensitivity Analyses

Sensitivity analyses to assess the robustness of the primary analysis results to missing data as outlined in [Appendix E Accounting for Missing Data](#), may be conducted utilising the FAS, unless otherwise specified, depending on the amount of missing data due to patients who prematurely discontinue study treatment and/or study participation.

In addition to the sensitivity analyses outlined in [Appendix E Accounting for Missing Data](#), the following analyses will also be performed:

- 1 The primary analysis will be repeated including only data from patients whilst being on study treatment ie, excluding data once patients discontinue from study treatment. For this analysis the patient's observed follow-up time will correspond to their actual "on-treatment" period defined as the period from first dose of study treatment (ticagrelor or

placebo) up to and including last dose of study treatment + 7 days. Refer to Section 3.1.7.1.

- 2 The primary analysis will be repeated where the response variable is the number of VOC events that occur during the defined treatment period, irrespective of the number of days between the onset of events.
- 3 The analysis will be repeated by replacing the factor for IxRS baseline hydroxyurea use (Yes/No) with a more inclusive indicator for hydroxyurea use defined as a combination of (a. and/or b.):
 - (a) IxRS baseline hydroxyurea use (Yes/No) **AND/OR**
 - (b) Hydroxyurea use:
 - (i) Start date after randomisation (Visit 2) AND
 - (ii) Duration of hydroxyurea use of at least 6 months during the study (latest stop date of hydroxyurea use record – earliest start date of hydroxyurea use record AFTER randomisation [Visit 2] + 1 [converted to months] \geq 6 months).
Where:
In case of ongoing medication use, study completion date, as collected on the disposition eCRF, or date of premature study discontinuation will be used to impute the latest stop date of hydroxyurea use in order to derive duration (months) within the context of the study.
If both these criteria (i) and (ii) are met the value will be “Yes”, otherwise it will be “No”.
- 4 The primary analysis will be repeated using the PP analysis set.
- 5 The primary analysis will be repeated for the following combination of covariates, if there are at least 5 patients within each stratum:
 - (a) Treatment group, baseline hydroxyurea use (Yes/No), age group at randomisation (Visit 2) (\geq 2 years to < 12 years, \geq 12 years to < 18 years)
 - (b) Treatment group, baseline hydroxyurea use (Yes/No), prior VOC events in previous 12 months prior to study enrolment at screening (Visit 1) (\geq 2 to \leq 4, > 4), as collected on the VOC eCRF
 - (c) Treatment group, baseline hydroxyurea use (Yes/No), and geographic region
 - (d) Where geographic region is defined as:
 - North and South America (USA, Canada, Brazil)
 - Europe (UK, Turkey, Spain, Italy, Greece, Belgium)
 - Africa and Asia (Egypt, Ghana, India, Kenya, Lebanon, South Africa, Tanzania, Uganda)

- (e) Treatment group, baseline hydroxyurea use (Yes/No), age group at randomisation (Visit 2) (≥ 2 years to < 12 years, ≥ 12 years to < 18 years), prior VOC events in previous 12 months prior to study enrolment at screening (Visit 1) (≥ 2 to ≤ 4 , > 4), as collected on the VOC eCRF, and geographic region
- 6 Zero-inflated Poisson and zero-inflated negative binomial models will be run on the same data as used for the primary analysis to allow for over dispersion seen in the negative binomial and Poisson models. The models allow for the excessive zero counts in the data. The zero-inflated Poisson and negative binomial models split the data into two separate distributions where one distribution (either Poisson or negative binomial) that generate both zero and non-zero counts, the second distribution is a constant distribution that generates only zero counts. When a zero count is observed, there is some probability, called the zero-inflation probability, that the observation came from the always-zero distribution; the probability that the zero came from the Poisson/negative binomial distribution is 1 minus the zero-inflation probability. When the underlying count distribution is a Poisson distribution, the mixture is called a zero-inflated Poisson (ZIP) distribution; when the underlying count distribution is a negative binomial distribution, the mixture is called a zero-inflated negative binomial (ZINB) distribution (Hilbe 2007).

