There are no other drugs approved for reduction of VOCs in children with SCD with a similar mechanism of action as ticagrelor. Hydroxyurea is approved for use in children with SCD in some markets and more recently, L-glutamine was approved by the US FDA. Evaluation of ticagrelor when given in addition to standard of care including these medications, where available and when considered medically appropriate, is considered acceptable for studying the efficacy and safety of ticagrelor in this patient group as compared with placebo.

Treatment duration is at least 12 months for study participants, but no longer than 24 months for any patients. The expected average follow-up is 18 months, assuming a uniformly distributed enrolment period of 12 months. Considering inclusion of patients with at least 2 VOCs in the past year, this treatment duration is considered long enough to evaluate effects on VOC events as well as to capture safety and tolerability data supporting a potential future long-term use of ticagrelor.

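### Sensitivity analysis 3 adjusts for hydroxyurea started after randomisation, so it is not a clean check of the treatment-policy result

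*SAP*

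**What the plan says.** The primary model (SAP 4.2.6.1) contains treatment, baseline hydroxyurea and a log follow-up offset. SAP 4.1.1 ties the hydroxyurea factor to the IxRS stratum on intention-to-treat grounds.

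Item 3 of SAP 4.2.6.3 refits that model by "replacing the factor for IxRS baseline hydroxyurea use (Yes/No) with a more inclusive indicator for hydroxyurea use defined as a combination" of two limbs. One is the IxRS baseline value. The other requires "Start date after randomisation (Visit 2) AND" at least 6 months of use during the study. Ongoing use is closed at study completion or premature discontinuation when the 6 months are counted. The covariates added in item 5 are all baseline factors.

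SAP Appendix E puts the primary analysis under a treatment-policy estimand: later alternative SCD treatments are part of the effect being estimated.

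The protocol says that hydroxyurea lowers the rate of painful crises and ACS (1.1), is not withheld during the trial (1.3), and that standard of care is adjusted at the investigator's discretion (1.4). Neither document says why a patient would start hydroxyurea, how many are expected to, or how large its effect is.

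**The concern.** A covariate fixed before randomisation cannot be altered by treatment. The second limb of item 3's indicator can be. If investigators start hydroxyurea in children who keep having crises, and ticagrelor prevents crises, more placebo than ticagrelor patients move from No to Yes, and those who move are high-rate patients. The model then credits part of the placebo excess to hydroxyurea rather than to treatment.

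What is at stake is how a robustness check is read. Item 3 sits among the analyses meant to support the primary result, names no estimand of its own, and removes part of what the treatment-policy estimand includes. If it differs from the primary result, the reader cannot tell a fragile finding from an artefact of the covariate. If it agrees, little has been tested.

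**Working it through.** **1. Reproduce the planned design, so that the check rests on the sponsor's own event model.** Protocol 8.2 gives the distribution: "The number of VOCs is assumed to have a negative binomial distribution with shape parameter 0.8". The same section sets a placebo rate of 2.0 crises a year, halved on ticagrelor, with equal allocation and at least 12 months on study. Protocol 1.2.2 adds the follow-up pattern: "The expected average follow-up is 18 months, assuming a uniformly distributed enrolment period of 12 months". I read the shape as a gamma shape, so the dispersion is k = 1/0.8 = 1.25, and take follow-up t as uniform on 1 to 2 years.

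Information per patient on the log rate is the mean of λt/(1 + kλt), which equals (1/k) × [1 − ln((1 + 2kλ)/(1 + kλ))/(kλ)].

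- Placebo, λ = 2, kλ = 2.5: 0.8 × [1 − ln(6/3.5)/2.5] = 0.628
- Ticagrelor, λ = 1, kλ = 1.25: 0.8 × [1 − ln(3.5/2.25)/1.25] = 0.517
- Variance with 77 per arm: (1/0.628 + 1/0.517)/77 = 0.0458, so SE = 0.214
- Power: Φ(0.693/0.214 − 1.960) = Φ(1.279) = 89.95%

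A simulation of 5,000 trials gave 89.8%. This matches the figure of about 90% that Protocol 8.2 states for a total of 154 at the two-sided 5% level. Reading 0.8 as the dispersion gives 96.4% and does not match. The dropout step also reproduces if 15% loss is assumed: 154/0.85 = 181.2, which rounds up to the planned 182.

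**2. The two models.** Both are log E(Y) = log T + b0 + b1·treatment + b2·H. In the primary model H is baseline use. In item 3, H = 1 for baseline use, or for a start at time S after Visit 2 with at least 6 months of use before follow-up ends at T. Baseline users and new starters share the single coefficient b2.

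**3. Dependence on remaining follow-up.** If use continues once started, a start counts only when T − S is at least 6 months. With T between 12 and 24 months the latest qualifying start falls between 12 − 6 = month 6 and 24 − 6 = month 18. Two children who both start at month 10 are coded differently if one has 12 months of follow-up (2 months of use, No) and the other 24 (14 months, Yes).

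**4. Simulation.** Events were generated in time from the step 1 model with a true ratio of 0.5 (1.0 in one row), and both models were fitted to the same large samples. Every hydroxyurea input is an assumption. Unless the row says otherwise, baseline users and non-users have equal rates.

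| Assumed pattern of starts | Primary model | Item 3 | Shift |
|---|---|---|---|
| One-off: 30-50% of non-users can start once, at the 2nd or 3rd VOC; hydroxyurea ratio 0.7 | e.g. 0.505; 0.502 | 0.513; 0.501 | about 0.00-0.01 |
| Chance renewed at every VOC from the 2nd or 3rd; hydroxyurea ratio 0.7 | 0.50-0.54 | higher throughout | about 0.02-0.05; up to about 0.08 in the heaviest settings |
| Chance 0.1-0.3 at every VOC; hydroxyurea ratio 0.5-1.0 (18 settings) | 0.50-0.54 | 0.51-0.59 | 0.01-0.06, toward 1 in all 18 |
| Starts unrelated to VOCs, or driven only by underlying severity equally in both arms | 0.50 | 0.50 | none |
| True ratio 1.0, starts triggered by VOCs (30% baseline use, 0.3 per VOC, hydroxyurea ratio 0.7) | 0.997 | 0.998 | none |
| Baseline users at 0.4-0.5 of the non-users' rate, chance 0.1 per VOC | 0.498; 0.502; 0.521 | 0.491; 0.493; 0.513 | −0.007; −0.009; −0.008 |

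**5. In trials of 154 patients.**

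- 60% baseline use, chance 0.2 per VOC: ratio 0.503 to 0.518, power 89% to 88%.
- 30% baseline use, chance 0.3 per VOC, hydroxyurea ratio 0.7: ratio 0.523 to 0.577, power 89% to 81%.
- True ratio 1.0: rejection 4.8% (primary) and 5.7% (item 3) in 600 runs. The simulation error is √(0.05 × 0.95/600) = 0.9 percentage points, so this shows no inflation.

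**6. After early termination.** SAP 3.1.4.1 ends the study at the stop communication. With follow-up assumed to run from 0.1 to 1.5 years, the shift was mostly 0.00-0.01 and at most about 0.02, because fewer starters can accrue 6 months.

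**7. The alternative.** Ending counts and follow-up at hydroxyurea start gave 0.49-0.51 against the true 0.5.

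**The case against.** The strongest reply has four parts.

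- **Mechanism.** A reader might infer that item 3 certainly adjusts for a consequence of the outcome and so must weaken a real effect. The documents do not support this: they never say why hydroxyurea is started. The table shows no shift when starts do not depend on VOCs and a small reversal in some settings. This part stands; the direction is probable, not established.
- **Size.** The shift depends on whether a patient has one chance to start or a new chance at each crisis, on baseline prevalence, and on follow-up that early termination has shortened. This stands too; any narrow figure would mislead.
- **Hydroxyurea coefficient.** In many settings it moves above 1, and a reader might infer that the trial would report hydroxyurea as harmful. SAP 4.2.6.1 does not list that coefficient among the results to be presented, so no planned conclusion rests on it.
- **Existing cover.** The primary model and the hydroxyurea subgroup use baseline values only. SAP 4.2.4 already counts patients who start after randomisation and stay on hydroxyurea for at least 6 months. This limits the consequence, but that table omits shorter use and does not change what item 3 estimates.

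None of this answers the structural point: the second limb is measured after randomisation, and the estimand it would serve is not named.

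**Conclusion.** The point holds in a limited form. Item 3 conditions on a post-randomisation variable that treatment and VOCs may influence and that depends on remaining follow-up, so it neither estimates the treatment-policy effect nor tests an assumption of the primary model. That follows from the SAP text alone.

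Direction and size rest on assumptions. If crises prompt hydroxyurea and ticagrelor works, the ratio probably moves toward 1, by the amounts in the first three rows of the table; how often crises lead to a start matters most. Under no treatment effect, with starts equally likely in both arms, there is no bias. The primary analysis is untouched, and the documents do not support reading this as a threat to the trial's main conclusion. It is worth correcting because the repair is small and the analysis as written is hard to interpret whichever way it falls.

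**What to change.** In item 3, keep the baseline hydroxyurea covariate and drop the inclusive indicator. In its place, add a supplementary analysis that treats hydroxyurea initiation as an intercurrent event and names its estimand. One example is a hypothetical estimand (no hydroxyurea started after randomisation), estimated by the primary model with counts and follow-up ended at hydroxyurea start. Label it as answering a different question from the treatment-policy analysis. Swapping the IxRS value for baseline use from the CM eCRF would not serve: that tests mis-stratification only.

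Extend the SAP 4.2.4 summary to all post-randomisation starts by arm, without the 6-month limit, so that any imbalance is visible. State how partial start dates are handled, since Appendix C sets a missing day to the first of the month.

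Cost: SAP wording, made before unblinding, and one reprogrammed supporting analysis; start dates are already collected on the CM eCRF. The new analysis has slightly less follow-up and assumes that ending follow-up at hydroxyurea start is explained by the observed history.
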